| Livelihoods Pathways including 1) On-Farm crop and livestock pathways (Target: 75% of SILC Group Members); 2) Off-Farm pathways for youth livelihoods diversification such as extension agents, value-add processing and production (Target: 20% of households); and 3) wage employment pathways for youth (Target: 5% of SILC Group Members). Each pathway has a detailed technical training curriculum delivered over a series of sessions; additional tailored markets and business skills trainings specific to each livelihood pathway. | Additional supports include: 1) Seven Steps of Marketing Training (Target: all on- and off-farm pathways); 2) Climate Smart Agriculture to reduce water needs and increase soil health and vegetation coverage (Target: 100% of On-Farm Pathway); 3) Producers Groups and linkages to markets/suppliers/buyers (Target: 20% of On-Farm Pathway); |
| Access to Finance via formal financial linkages to service providers and capacity building for providers (Target: 70% of on- and off-farm pathway) | Selected financial institutions will be provided with a credit guarantee fund and capacity building support to help facilitate loans. Private sector value chain assessment and financing [to address bottlenecks]. Additional private sector engagement (agro-dealers, SILC providers, animal health) and linkage facilitation. |
| Livelihoods Transfers of US\$300 for the poorest 30% of PSNP public works households. | Youth Transfers of \$250 for 20% of youth 18-29 (poorest and volunteer) participating in the on- and off-farm pathways. |

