A subset of kebeles (n=70) was randomly allocated to Ifaa Basic and Ifaa Enhanced Packages as part of a cross-RFSA learning activity (USAID is supporting similar projects in other regions of Ethiopia) that is supported by the funder, USAID Bureau of Humanitarian Affairs. This effectiveness evaluation leverages this randomization to compare the two intervention packages. Additionally, 50% of kebeles were selected for livelihoods interventions, which occur in both Basic and Enhanced kebeles; livelihoods kebeles were selected based on criteria developed by CRS, but assignment to the enhanced vs basic package was random. Finally, approximately half of Ifaa Project kebeles are 'the free zone' where there is flexibility in intervention packages of the course of the project.¹ The distribution of the three Ifaa intervention packages that will compare in the proposed effectiveness evaluation is presented in **Table 2** below.

Table 2: Ifaa Intervention Allocation by Administrative Area

| Woredas/Districts Intervention Package | Study Eligible Kebeles/Sub-Districts* | | |
|---|---------------------------------------|---|--|
| | Ifaa Basic (n=25) | Ifaa Enhanced (n=34) | Ifaa Enhanced + Livelihoods (n=35) |
| Babile | Gemechu Ifa Jalale | Lekolo Shek husen Tofiq Tuluhoro | Erer guda Gambela Ibada gemechu Nejata gemechis |
| Chinaksan | Chelchale Kobobika | Biftuu Waree Gela | Amola Baduelemo |

¹ These kebeles were not considered in the sampling frame because of the high risk of contamination.

| | Migira | Kaleroga | Dawe kora |
|-------------|---|--|---|
| | Tiro gudoo Wachuhulet | Orda sost Tirosendare | Dembesele Kocher Merer Mudi dawe |
| Deder | Burka Berekha Mumicha Nedi gelansedi | Gegewisa Haremlemekuni Huffe Kura deder Lemen welteha | Burka Geba Cheka gemechu Chela Negeya Golu Oda kebena Welteha gudina |
| Fedis | Bareda Bedatu | Bid Borra Efitu dada Negaya bobasa Risiki | Ido Baaso Kerensa lencho Umer kule |
| Gursum | Ebsa Hariro Misira Saqabadii | Berite Gara wadaja Gefire guda Goro siyo Kebso Negeya | Awdal Day feres Harashi Kasa oromiya Oda oromiya |
| Jarso | Aneno mite Burka mete Debub debelo | Amen Epa jalela Gidiya licha Oda muda | Afgug Chala Gara abdula |
| Melka Belo | Fule negeya Haka mulisi Tokuma bilisumu | Bifitu negeya Daba kenisa Mulisa hakwa Tokuman kane | Chefe Jeneta Dire Qufa Welikituma bilusuma |
| Midega Tola | Ibiro musa Terkafeta | Kerensa Mukura | Bilisuma Biyo waraba Lencha Roba |

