- (2) **Cluster Selection.** Within each kebele, the three largest communities and/or population concentrations from within each kebele will be selected as cluster start locations. This approach was identified to account for inclusion criteria, notably that households must have a pregnant woman or a child <36 months of age, which reduces the number of households that are eligible for study participation.⁵ Once start locations have been identified, all beneficiary lists will be verified, and households that meet inclusion criteria will be enumerated. This process will occur immediately prior to the start up of data collection in the kebele. If fewer than 20 eligible households are identified in the community, enumeration will continue in adjacent communities until the target sample size is identified.
- (3) **Household Selection.** Data collection will begin within several days of the household enumeration exercise. Households will be sampled from the lists of beneficiaries that are verified as meeting inclusion criteria. In some cases, this may be exhaustive (e.g. in kebeles with small populations where adjacent communities needed to be visited to identify the target number of households). In larger kebeles or communities where the number of eligible households exceeds the target sample, a systematic list-based sampling approach (i.e. every n^{th} household) will be used. Replacement sampling will be used until the target number of households in each location are enrolled.

B. Sample Size

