| Poor or borderline household food consumption (FCS) | 48% in E Hararghe (UMN , 2020) | -10% | 609 | 1827 | |
| | | -12% | 402 | 1206 | |
| Minimum dietary diversity among children <5 years | | -8% | 1070 | 3210 | |
| | | -10%* | 674 | 2022 | |
| | | -12% | 481 | 1443 | |
| 19.5% in Oromya (2019 DHS) | +8% | 785 | 2355 | | |
| | +10% | 533 | 1599 | | |
| | +12% | 366 | 1098 | | |

*denotes Ifaa change target

C. Does your study meet the NIH definition of “clinical trial”: “A research study in which one or more human subjects are prospectively assigned to one or more interventions (which may include placebo or other control) to evaluate the effects of those interventions on health-related biomedical or behavioral outcomes”?

Per the JHSPH IRB’s determination, this study meets the definition of a clinical trial.

IV. Participants:

A. Inclusion Criteria:

- Households are PSNP clients
- Households are Ifaa Project beneficiaries that are planned participants in: 1) SILC groups (Ifaa Basic); 2) SILC Groups AND Care Groups (Ifaa and Enhanced); or 3) SILC groups AND Care Groups AND a Livelihoods Pathway.
- Households have a pregnant woman OR at least one child <36 months of age
- Households have an adult member that is capable of giving informed consent and completing an interview

B. Exclusion Criteria:

- Child headed households (all members age 17yrs or less)
- Individuals not mentally able to give informed consent and complete an interview

V. Study Procedures:

A. Recruitment Process:

1. *Describe how you will identify, approach, and inform potential participants about your study. Include details about who will perform these activities and their qualifications.*

The JHU team will receive the list of PSNP households/Ifaa beneficiary households living in the sampled Ifaa Kebeles from CRS Ethiopia team. Trained enumerators will conduct a verification exercise and visit households on the list to confirm eligibility. After the verification exercise, a second visit will be made to selected households where enumerators will explain the study purpose, households will have the opportunity to ask questions, and oral consent will be obtained. Any adult household member will be eligible to participate, however, preference will be given to caretakers of young children/pregnant women followed by household heads.

2. *Address any privacy issues associated with recruitment.*

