The recruitment procedure is expected not to put the potential study populations at risk. The study topic is not sensitive in the population and PSNP and Ifaa beneficiary status is already known among communities.

B. Consent Process:

1. *Describe the following details about obtaining informed consent from study participants. If a screening process precedes study enrollment, also describe the consent for screening.*

a. Who will obtain informed consent, and their qualifications:

A private Ethiopian data collection firm will be contracted to conduct the two household surveys. The data collection firm will use experienced interviewers. Prior to data collection, interviewers will be trained on the consent process and the data collection tool; training will be co-led by a JHU research team member.

b. How, where, and when the consent discussion(s) will occur:

The consent discussion will occur at the beginning of the home visit for the enrollment interview. The enumerator will identify a quiet and private place in or near the household so that privacy can be maintained and interruptions avoided. The enumerator will read the consent statement aloud to prospective participants. They will have an opportunity to ask questions and discuss participation with the interviewer prior to consenting to participate.

c. The process for determining whether a potential participant meets eligibility criteria. If you will collect personally identifiable information for screening purposes, collect only data needed for this purpose and explain what will happen to the data for individuals who are not eligible:

As described above, Ifaa beneficiary lists will be used for recruitment. Households on the list will be reviewed by Ifaa staff, government extension workers and/or enumerators prior to the start of data collection to determine if households are eligible, and if eligibility is unknown household visits will be conducted to verify eligibility.

d. Whether you will obtain a signature from the participant or will use an oral consent process:

Oral consent will be used due to high levels of illiteracy.

e. Whether you will obtain a legally authorized representative's signature for adults lacking capacity:

We do not plan to enroll individuals lacking capacity.

f. If children are included in the study, if and how you will obtain assent from them:

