The outcome variables of focus at the household level will be measures of food security, including 1) [Food Consumption Score](#), 2) [Household Hunger Scale](#), and 3) [Coping Strategies Index](#). At the individual level, outcome variables of focus will include 1) [Infant and Young Child Feeding Indicators](#) (in particular achievement of minimum dietary diversity); and 2) prevalence of stunting and wasting, in accordance with the [World Health Organization Child Growth Standards](#). Background information on individual (e.g. literacy, age, pregnancy status) and household characteristics (e.g. size, residence location) will also be collected so that these can be controlled for or used for disaggregation in data analysis. All outcomes will be analyzed as continuous variables and as categorical variables based on pre-determined thresholds.

A descriptive analysis of household sociodemographic characteristics and outcome measures will be performed. Continuous variables will be presented as mean (SD) and categorical variables as n (%). ANOVA tests will be conducted for baseline characteristics and primary and secondary outcomes to examine the comparability between the three and intervention groups; individual/household characteristics with significant differences between groups at baseline will be controlled for in models that estimate the effect of the interventions.

The program effect on expected primary outcome measures will be estimated using mixed-effect linear regression analysis for continuous outcomes and Generalized Estimation Equation (GEE) model for binary outcomes. In the mixed-effects models, the random effect component included indicators to control for clustering at school levels. The fixed component included the intervention group (intervention vs. control), time and an interaction term for group and time. The GEE models will be used to examine binary outcomes with longitudinal data from both enrollment and endline. These models will estimate the change in a binary outcome among members of a given intervention group from enrollment to endline, compared to the change in the same outcome in the control. The GEE models also included an interaction term between the intervention group and time (baseline/endline).

5. **Answer the following if they are relevant to your study design:**

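### Entry depends on planned participation in each arm's own package, so households are filtered by a different rule in each arm; the bias is probably modest but avoidable

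*Combined protocol and SAP*

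**What the plan says.** The participation bullet in Section IV.A sets three nested conditions. Households must be "planned participants in: 1) SILC groups (Ifaa Basic); 2) SILC Groups AND Care Groups (Ifaa and Enhanced", or, in the third arm, planned for "SILC groups AND Care Groups AND a Livelihoods Pathway". All arms also require PSNP client status and a pregnancy or a child under 36 months.

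Section III.A, step 3, makes these criteria the sampling frame: "Households will be sampled from the lists of beneficiaries that are verified as meeting inclusion criteria". On who checks them, Section V.B.1.c says: "Households on the list will be reviewed by Ifaa staff, government extension workers and/or enumerators prior to the start of data collection". No section says how planned participation is decided. None says how to find Basic households that would have been placed in a Care Group, or Basic and Enhanced households that would have been placed in a pathway.

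On allocation, Section II says: "livelihoods kebeles were selected based on criteria developed by CRS, but assignment to the enhanced vs basic package was random". Section V.C, item 5A, instead describes the sites as purposively allocated by the implementing partners.

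On analysis, Section V.C says "individual/household characteristics with significant differences between groups at baseline will be controlled for in models that estimate the effect of the interventions", and its models include a group-by-time interaction.

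**The concern.** Randomising kebeles balances the kebeles' whole populations. It does not balance subsets picked out by a rule that changes with the arm. The Care Group condition applies in Enhanced but not in Basic, so it touches the contrast for which the plan relies on randomisation. The pathway condition applies only in Enhanced + Livelihoods. There it is a second selection on top of implementer-chosen livelihoods kebeles.

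If households marked for a Care Group or a pathway would have changed differently over 24 months anyway, that difference is counted as a package effect. The planned analysis removes only part of it. Covariate adjustment covers measured characteristics that reach significance at baseline, and the group-by-time term removes stable differences in level. Neither handles unmeasured differences in trend, such as readiness to take up an enterprise.

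**Working it through.** **The benchmark.** Section III.B states 915 to 1,070 households per group for an 8-point change in poor or borderline FCS. I used the pooled two-proportion formula (two-sided 0.05, 80% power), multiplied by 1.5 for the design effect and 1.2 for loss:
- 34% to 26%: 514 x 1.5 x 1.2 = 925 (stated 915).
- 48% to 40%: 604 x 1.5 x 1.2 = 1,087 (stated 1,070).

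Both agree within 3%, so I take 8 points as the plan's own yardstick. Correcting eligibility does not itself change this calculation.

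**Bias formula.** Let M be the mean untreated change among households meeting the extra condition, and N the mean among otherwise eligible households that do not. The filtered arm has mean M. The unfiltered arm has c x M + (1 - c) x N. The difference is (1 - c) x (M - N) = (1 - c) x d.

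**Range for d.** The documents do not give it. I assume 3 to 10 points. The top of the range equals the project's whole FCS change target (10 points, Table 3), so it is high for a difference in untreated change.

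**Pathway condition (Table 1).** The on-farm target is "Target: 75% of SILC Group Members", the wage target is "Target: 5% of SILC Group Members", and off-farm is 20%, stated as a share of households.
- Same base, no overlap: 75 + 20 + 5 = 100%.
- On-farm and wage only, no overlap: 75 + 5 = 80%.
- Full overlap with on-farm: 75%.

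So c is about 75 to 100%, if the targets for SILC members also hold for households with a pregnancy or young child. At c = 75%, the bias is 0.25 x 3 = 0.75 to 0.25 x 10 = 2.5 points. At c = 80% and d = 10 it is 2.0. At c = 100% it is 0.

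**Care Group condition (footnotes 2, 4 and 5).** No coverage target is given. One group reaches 10 x 10 = 100 to 15 x 15 = 225 neighbours. The right comparison is with eligible households in a kebele, not with the 60 sampled (3 clusters x 20). Footnotes 4 and 5 imply 75 x 15% = about 11 to 650 x 25% = about 163 eligible. In most kebeles c may therefore be near 100%, and the shared pregnancy or young-child criterion points the same way. In the largest kebeles, one group at the low end gives c = 100/163 = about 61%, assuming one group per kebele with its places spread evenly. The bias is then 0.387 x 3 = 1.2 to 0.387 x 10 = 3.9 points.

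**Both conditions.** Basic vs Enhanced + Livelihoods carries both filters, so the terms add. The extreme corner is 3.9 + 2.5 = 6.4 points. It needs the lowest coverage on both conditions, d = 10 twice, and the same direction.

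**d needed for a full 8 points.** Pathway: 8/0.25 = 32 points at c = 75%, or 8/0.20 = 40 at c = 80%. Care Group at c = 61%: 8/0.387 = about 21.

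**Effect on false positives.** Effective households per arm are 1,080 x 0.8/1.5 = 576. Take prevalence as 48% at baseline and 40% at endline. The standard error of the difference in change, ignoring within-household correlation, is sqrt(2 x (0.2496 + 0.24)/576) = 0.0412. For an endline comparison it is sqrt(2 x 0.24/576) = 0.0289. The two-sided error is 1 - Phi(1.96 - b/SE) + Phi(-1.96 - b/SE):

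| Bias b | Change | Endline |
|---|---|---|
| 1 point | about 6% | about 6% |
| 2.5 points | about 9% | about 14% |
| 3.9 points | about 16% | about 27% |

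**The case against.** The strongest reply is that the bullet describes each arm's beneficiaries and is not a filter. Recruitment starts from general PSNP and Ifaa beneficiary lists, and baseline precedes intervention start-up. Section III.A describes enrolled households only by pregnancy or child age. Footnote 5 derives its 15 to 25% eligibility estimate from child-age data alone. This reading is possible. But the bullet stands under Inclusion Criteria, and field teams are told to verify lists against those criteria, so the plan followed as written does filter. If description was meant, the text still needs changing.

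A second reply is that the effect is near zero: Care Groups serve mothers whom the common criterion already selects, and the pathway targets may sum to 100%. That may well be so, and it limits the severity. It is not assured, because neither coverage figure is given for the study population.

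A third is that purposive kebele selection, and the allocation wording in Section V.C, item 5A, threaten comparability more than a household filter does. That is fair, but those problems do not remove this one.

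In the other direction, a reader might infer that the filter invalidates the Basic vs Enhanced comparison, or could by itself produce an 8-point effect. The documents do not support that: d would have to be about 21 points or more on one condition alone. Nor do they show that staff who knew the package used their discretion to favour an arm. They only leave the rule unstated.

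**Conclusion.** The concern holds in a limited form. As written, households enter under a different rule in each arm, and nothing in the design or analysis equalises them. At an assumed d of 3 to 10 points, the bias is 0 to 2.5 points for the pathway condition. For the Care Group condition it is 0 to about 1.2 points at d = 3, and 0 to about 3.9 at d = 10. The Care Group upper figures apply to the largest kebeles, not to the average. A result could be distorted, but one is unlikely to be created by this alone.

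The sizes rest on three assumptions: the range for d, Table 1 targets carrying over to households with a pregnancy or young child, and at least one Care Group per kebele. The sponsor should act because the central correction is cheap. The correction would not make Enhanced vs Enhanced + Livelihoods a randomised comparison.

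**What to change.** **Entry rule.** Use one rule in all three arms: PSNP client, Ifaa beneficiary, planned SILC participant by the same criteria fixed before start-up, and a pregnancy or a child under 36 months. Remove the Care Group condition. This costs almost nothing where coverage is near complete; elsewhere the estimate averages over households not reached. Do not rely on recording would-be Care Group status: it may not be observable in Basic kebeles, where no volunteers are selected.

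**Pathway condition.** Choose one:
- (a) Apply the same documented pre-intervention targeting criteria in every arm. There is little dilution, but at c = 75 to 80% another 20 to 25% of households are screened out in Basic and Enhanced. Footnote 4 already doubts that small kebeles can supply 60.
- (b) Drop it, and record at the planned list verification in every arm whether each household meets those criteria. Analysed in full, a 10-point pathway effect dilutes to 7.5 to 8.0 points (sample size factor 1/0.75² = 1.78 to 1/0.80² = 1.56). Restricted to households meeting the criteria, 810 to 864 of 1,080 per group remain. The 8-point detectable difference becomes 8 x sqrt(1/0.80) = 8.9 to 8 x sqrt(1/0.75) = 9.2.

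**Analysis.** Analyse by kebele assignment. Use actual participation from the endline module only in a secondary analysis.

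**If enrolment is complete.** Baseline was planned for May 2023 and this version is dated June 12, 2023. If households are already enrolled, record which rule was applied, classify households in all arms by the same targeting criteria from baseline data, and report the limitation.

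**Text.** If the bullet is descriptive, reword it so that it cannot act as a filter. Reconcile the purposive allocation in Section V.C, item 5A, with the random assignment in Sections II and III.A. Reconcile the SILC requirement in every arm with Table 1, which lists SILC under livelihoods, and with Figure 1, which shows two arms without livelihoods programming. State that Enhanced vs Enhanced + Livelihoods is a non-random comparison.

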As noted in Figure 1, the study includes three of the possible four Ifaa intervention combinations. Characterizing the impact of livelihoods programming without the Ifaa enhanced intervention was not considered a priority.

Figure 2. Study Flow Diagram

A longitudinal cohort design will be used to compare the effectiveness of three Ifaa intervention packages among PSNP beneficiaries: 1) the Ifaa basic package; 2) enhanced package without livelihoods; and 3) enhanced package with livelihoods. Under this approach, the enrolled households will have either a pregnant woman or children <36 months of age. Households will be followed over a two-year period, with the baseline and endline survey conducted at a similar time

³ Community led complementary feeding sessions (CCFLS) is a six month program targeted at children at risk of acute malnutrition or recently discharged from a malnutrition treatment program. It includes caregiver training on child feeding practices and growth monitoring and is a six month intervention, with intensive services/training in the first month and follow up monitoring.

period in the calendar year to avoid seasonal changes in food security. The magnitude of change in key indicators over time will be assessed for each group; if needed, adjusted models will be used to account for baseline differences between groups. Outcome measures of focus are aligned with Ifaa indicators and include measures of household food consumption and child diet. To ensure adequate geographic coverage, a **stratified sampling design** will be used as follows:

- (1) **Kebele Selection.** Two kebeles per intervention arm will be purposively selected in each of the nine woredas with the aims of 1) of maximizing geographic similarity in terms of agro-ecological zone (lowland, midland, highland) and remoteness; and 2) ensuring sufficiently large beneficiary population is available for sampling purposes. In the case of smaller kebeles where it appears unfeasible to attain three clusters, the sample may be distributed across additional kebeles within the woreda.⁴

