The primary outcome measure for the evaluation is improvement in household food security. To align the evaluation with project aims, key project indicators are used as study outcome measures. These include: 1) At the household level, **Poor or Borderline Food Consumption Score (FCS)**; and 2) at the individual level, change in **minimum dietary diversity among children <5 years**. Sample size calculations are presented in **Table 3** (following page) and are based on both primary and secondary outcome measures for within-group change over time using available data from the Ifaa baseline along with Ifaa targets for change. Assumptions included the following: 1) power ($1-\beta$) of 80% and significance of $\alpha=0.05$; 2) a design effect of 1.5 to take into account differences across Kebeles; and 3) expected absolute change in proportion of primary/secondary outcome; and 4) loss to follow up rate of 20% over the study period. Based on initial sample size projections, a minimum sample size of 915-1,070 households per group and 2,745-3,210 is required which is sufficient to detect differences $\geq 8\%$ between groups for both the primary and secondary outcome measures.

We are proposing a planned sample size of 1,080 per group or 3,240 households total. Given challenges in field coordination across multiple teams and delays in data quality monitoring reviews, it is possible that several additional households could be enrolled in a kebele. To ensure that the approved sample size is not inadvertently exceeded due to communication challenges we are requesting approval for a **maximum sample of 3,500 households**.

Table 3: Sample Size Calculations

| | Baseline Value | Magnitude of Change | Sample Size per Group | Total Sample Size |
|--|----------------------------|---------------------|-----------------------|-------------------|
| | 34% in Oromiya (WFP, 2021) | -8% | 915 | 2745 |

⁴ The number of beneficiary households per kebele ranges from approximately 75 to 650; given inclusion criteria it is unlikely that smaller kebeles will have 60 eligible households, in which case cluster(s) will be assigned in additional kebeles in the woreda.

⁵ In the baseline survey, the average number of children <5years in PSNP households was 0.83 and 14% of the population was <5 years of age. Based on this we estimate that 15-25% of Ifaa beneficiary households will meet study inclusion criteria.

| | | | | | |
|---|---|-------|------|------|--|

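### Covariates are chosen by baseline significance and their place in the model is not stated; a short list fixed before endline, entered with time interactions, would target confounding of change better

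*Combined protocol and SAP*

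**What the plan says.** In the combined protocol and SAP, the data analysis plan (Section V.C, item 3) sets the screen: "ANOVA tests will be conducted for baseline characteristics and primary and secondary outcomes". It then gives the consequence: "individual/household characteristics with significant differences between groups at baseline will be controlled for in models that estimate the effect of the interventions". No significance threshold, candidate list or allowance for clustering is stated for this step. Background variables appear only as examples (literacy, age, pregnancy status, household size, residence location).

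For the mixed-effects models the same item says: "The fixed component included the intervention group (intervention vs. control), time and an interaction term for group and time". The GEE models for binary outcomes also carry a group-by-time interaction. No covariate-by-time term is mentioned, and nothing says whether covariates enter as main effects or otherwise.

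Section III.A is looser: "if needed, adjusted models will be used to account for baseline differences between groups".

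On how groups come to differ:
- Section III.A: "Two kebeles per intervention arm will be purposively selected in each of the nine woredas", with one stated aim being "maximizing geographic similarity in terms of agro-ecological zone (lowland, midland, highland) and remoteness".
- Section II: "livelihoods kebeles were selected based on criteria developed by CRS", while assignment to the enhanced or basic package is described there as random.
- Section V.C, item 5.A describes the selected sites as purposively allocated to the three packages.
- Section IV.A: planned participation in programme components, which is part of eligibility, differs by arm.

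**The concern.** The target of the analysis is the difference between groups in change from baseline to endline. A baseline variable confounds that target if it differs between groups and also predicts change. A baseline significance test addresses only the first condition, and does so through sample size: it can miss a real imbalance and flag a chance one. It says nothing about the second.

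The form of adjustment matters as much as the choice of variable. A time-invariant characteristic cancels out of each household's own change. Entering it only as a main effect therefore gives the appearance of control without altering the estimate of interest.

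Real group differences are plausible, chiefly for the livelihoods arm. What is at stake is a model settled by a weak criterion, and an adjustment that may do nothing for differential change.

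**Working it through.** **Plan figures used.** 1,080 households per group, a design effect of 1.5, and an 8-point change (Section III.B). The plan gives no figure for the covariate rule itself. Its sample-size range reproduces approximately: the two-proportion formula (two-sided 5% assumed, 80% power) × 1.5 × 1.2 gives 514 × 1.8 = 925 for 34% to 26% (plan: 915) and 604 × 1.8 = 1,087 for 48% to 40% (plan: 1,070). The 1.5 belongs to that outcome calculation ("a design effect of 1.5 to take into account differences across Kebeles"). Applying it to a covariate is my assumption.

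**1. Chance flags.** For a three-group test at nominal 5% that ignores clustering, with between-arm variance inflation D, the probability of flagging a truly balanced characteristic is 0.05^(1/D).
- D = 1: 5%. D = 1.5: 13.6%. D = 2: 22%. D = 3: 37%.
- Arms are balanced within woreda, which lowers D. With 1,080/18 = 60 households per kebele, ICC = 0.5/59 = 0.0085. If a share f of the ICC lies between woredas, D = 1 + 59·ICC·(1−f) − f·ICC. For f = 25%, 50%, 75% (assumed), D = 1.373, 1.246, 1.119 and the rate is 11.3%, 9.0%, 6.9%.

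**2. Missed imbalance.** Take a characteristic at 50% with spread s between the extreme groups. P(not flagged) = P(noncentral χ² on 2 df < 5.99/D). The noncentrality is 1,080 × 2 × (s/2)²/(0.25·D) if the third group lies midway, and 1,080 × (2/3) × s²/(0.25·D) if two groups are equal and one differs.

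| Spread | Third group midway, D = 1 to 1.5 | One group differs, D = 1 to 1.5 |
|---|---|---|
| 3 points | 78% to 69% | 72% to 64% |
| 5 points | 46% to 43% | 33% to 33% |
| 10 points | 0.9% to 2.4% | 0.1% to 0.5% |

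**3. Bias in change.** Bias = imbalance × difference in change between levels of the characteristic. With change differing by 10 points (assumed):
- 3-point imbalance: 0.03 × 10 = 0.3 points (0.3/8 = 3.75% of the 8-point change)
- 5-point imbalance: 0.05 × 10 = 0.5 points (6.25%)
- 10-point imbalance: 0.10 × 10 = 1.0 point (12.5%)

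**4. What each form of adjustment does.** Two arms, true effect zero, 40% versus 50% with the characteristic, change differing by 10 points between levels.

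| Model | No covariate | Main effect | With time interaction |
|---|---|---|---|
| Linear, group-by-time | −0.0100 | −0.0100 | 0.0000 |
| Logistic, independence working correlation (link assumed), log-odds | −0.0415 | −0.0427 | 0.000 |

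The linear result is algebraic with complete data. In simulation with 20% random loss to follow-up, the main effect still removed essentially none of the bias.

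**The case against.** **The two complaints are alternatives.** If covariates enter as main effects, it hardly matters which ones the screen picks, because the linear estimate does not move. If they enter with time interactions, selection matters but the main-effect complaint falls. This stands, and the sizes must not be added. The 0.3 to 0.5 points belong to selection; the 1.0 point belongs to the unstated form, since the rule would nearly always flag a 10-point imbalance.

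**The screen uses baseline data only.** This stands. A reader might infer that covariates could be chosen to suit the endline result. The stated rule does not support that: it looks at baseline, two years earlier, and the list could be settled before endline. The fault is the criterion.

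**The plan does not say main effects only.** Correct: it is silent. A reader might infer that adjustment is bound to fail; the text supports only that no time interaction is stated.

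**Geography is not ignored.** Woreda is balanced by design, zone and remoteness are targets for similarity, and residence location is among the variables collected so that it can be controlled for. What remains is that adjustment for geography is not assured.

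**Basic versus Enhanced is described as random.** Section II says so, and Section III.A restricts the study to randomised kebeles. A reader might infer that the whole comparison is confounded; those sections do not support that. Section V.C, item 5.A describes purposive allocation, so the passages must be reconciled.

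**13.6% is not a ceiling.** It depends on carrying the outcome design effect over to covariates, and larger design effects give more.

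**Conclusion.** The concern holds in a limited form. Baseline significance is the wrong criterion for choosing covariates in a comparison of change, and the plan leaves open whether the adjustment can act on change at all. It bears most on the livelihoods contrast.

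The expected size is modest: a few tenths of a point for imbalances the rule commonly misses, and about one point for a 10-point imbalance adjusted by main effect only, against the 8-point change the study is sized for. These sizes rest on an assumed prevalence of 50%, assumed imbalances and an assumed 10-point difference in change. A characteristic that does not predict change would produce little bias under any form of adjustment.

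A reader might take the 1.0 point as bias shown in this study. The documents give no imbalance and no relation to change, so they do not support that. The change is worth making because it is cheap and removes an avoidable choice.

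**What to change.** Delete the significance-based rule in Section V.C, item 3 and the conditional adjustment in Section III.A. Any ANOVA that is kept should be descriptive and play no part in choosing covariates. Suggested wording:

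> All effect models will include one covariate list, fixed before endline data are seen: woreda, agro-ecological zone, and a few collected household characteristics justified as prognostic (for example household size and caretaker literacy), plus child age and sex for child outcomes. Each enters with a time interaction. The unadjusted group-by-time estimate will be reported alongside.

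Include remoteness only if a measure is defined before endline and derived before identifiers are deleted (Section VI, items 4 and 11). The plan names remoteness but gives no measure. Reconcile the descriptions of allocation in Section II and Section V.C, item 5.A.

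**Cost.** No new household questions are needed and the sample size is unchanged. Zone must be recorded for each kebele. The price is more model terms. With nine woredas there are 9 × 3 × 2 = 54 kebeles, leaving 54 − 3 − 8 − 2 = 41 kebele-level degrees of freedom after arm, woreda and zone. With the eight woredas legible in Table 2 there are 48 kebeles, leaving 48 − 3 − 7 − 2 = 36. Remoteness would take one more (40 or 35). Where zone hardly varies within a woreda, its term adds little. The list should stay short, and it can act only on measured characteristics.
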